1 PROTOCOL SUMMARY

1.1 SYNOPSIS

Title:	TRC-PAD Program: In-Clinic Trial-Ready Cohort (TRC)
Study Description:	Development of a large, well-characterized, biomarker-confirmed, trial-ready cohort to facilitate rapid enrollment into AD preclinical/prodromal trials utilizing feeder registries into the APT Webstudy and subsequent referral to in-clinic evaluation and biomarker confirmation. Participants with known biomarker status may have direct referral to the trial-ready cohort.
Objectives:	1. To build an efficient and sustainable recruitment system in order to enroll an initial TRC-PAD Cohort. 2. To optimize an innovative, adaptive risk algorithm to efficiently identify the most appropriate trial participants. 3. To develop and validate web-based cognitive and functional outcome measures for future clinical trials.
Study Population:	At least 2,000 (1,000 preclinical + 1,000 prodromal AD) trial-ready individuals aged 50-85
Description of Sites:	Approximately 60 AD clinical trials sites
Description of Study	No intervention
Intervention:	
Study Duration:	5 years
Participant Duration:	5 years

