3 OBJECTIVES AND ENDPOINTS

Aim 1: To build an efficient and sustainable recruitment system in order to enroll and retain an initial TRC-PAD Cohort. This approach will markedly accelerate recruitment timelines, shorten time to site activation for trials, and reduce unexplained variance in pre-trial cognitive testing, as compared to current recruitment approaches.

Aim 2: To optimize an innovative, adaptive risk algorithm to efficiently identify the most appropriate trial participants. Once optimized, this algorithm will be able to select amyloid positive individuals (and eventually tau and other neurodegenerative biomarkers) with >75% accuracy, greatly reducing future costly biomarker screen fails.

Aim 3: To develop and validate web-based cognitive and functional outcome measures for future clinical trials. Baseline and longitudinal cognitive performance (including lack of practice effect on repeated web-based cognitive tests), decline on performance based functional measures, and a combination of self- and study-partner report will predict and subsequently track with in-person measures of cognitive (PACC) and functional (CDR-SB) decline.

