9 STATISTICAL CONSIDERATIONS

All statistical analyses will be based on a pre-specified statistical analysis plan (SAP). This plan will be informed by preliminary data analysis done mid-way during the study to identify the presence of potential sources of bias, including but not limited to the distribution and nature of the data, confounding effects, and amount and type of missing data. Each metric of interest will be initially assessed descriptively. For categorical data, we will use rates as the outcome measures, excluding the missing and unknown cases. For continuous data, parametric (one-sample t-test), non-parametric (Wilcoxon signed rank test) or resampling approaches (bootstrap or jackknife techniques) will be used, as appropriate. Comparisons between metrics from recent, current-technology trials and the TRC-PAD metrics will be made using 95% confidence intervals. A p-value of 0.05 will be used to conclude significant differences between the two study groups. For comparisons of metrics across different sub-groups of interest, t-tests, chi-square tests or resampling techniques will be used, as appropriate for the type (continuous, categorical) and distribution (normal, non-normal) of the data. Regression models (generalized linear models or generalized linear mixed models), as appropriate, will be used to examine associations of covariates of interest with the TRC-PAD metrics.

All statistical analyses will be conducted at the end of the grant cycle with all available data at the point of data cut-off date. Due to the exploratory nature of these aims, no adjustments will be made for multiple comparisons. However, data will be reported as point estimates and confidence intervals to provide the magnitude and variability around each of the estimates. All analyses will utilize R (www.r-project.org).

Statistical Aim 1: This approach will markedly accelerate recruitment timelines, shorten time to site activation for trials, and reduce unexplained variance in cognitive testing.

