Analysis Plan: The use of adaptive approaches to participant selection, data capture and data monitoring will continually optimize the approach. At the end of the five years, formal tests of hypotheses will be conducted to assess the success of the web-based mechanisms by quantitative and qualitative analysis, in particular comparing timelines, cost, screen failure rates and the measured change and variance in cognitive scores to those in preclinical and prodromal studies for which similar data can be obtained. Two-sided, one-sample tests of means (recruitment timelines and time to site activation) or variances (variance in cognitive testing) or corresponding resampling techniques will be used to detect differences between the TRC-PAD sample and comparator data.

Power Analysis: Power analyses for these hypotheses were done using a two-sided, one-sample t-test for means and a one-sample test of variance using the software PASS. A reduction of 10% in mean recruitment timeline, mean time to site activation and unexplained variance in cognitive testing is considered scientifically meaningful. While the sample size selected was based on the need for a Cohort sufficiently large to support an efficacy trial, we have examined the power of this sample to test our hypotheses. 1. A sample size of 2000 participants achieves 90% power to detect a change as little as 3 days (3%) in recruitment timelines and time to site activation for trials,

assuming current estimates of 120+/-40 days respectively. 2 Estimates of baseline variability from completed AD trials range between 4.5 and 10 points in ADASCog11 score within a site. A sample size of 2000 participants achieves 90% power to detect a difference of at least 0.4 points (5% change) in unexplained standard deviation of cognitive scores, assuming a type I error rate of 5%. Thus, there is adequate power to detect very small differences and looking at multiple sub-groups of interest would not compromise power.

Statistical Aim 2: Once optimized, this algorithm will be able to select amyloid positive individuals (and eventually tau and other neurodegenerative biomarkers) with >75% accuracy, greatly reducing future costly biomarker screen fails.

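### Aim 1 claims lower unexplained variance, but the named variance test has no residual model or stage term, so stage mix can hide or mimic the 10% target

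*Combined protocol and SAP*

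**What the plan says.** The target is worded consistently. Section 3 (Aim 1) says the approach will "reduce unexplained variance in pre-trial cognitive testing, as compared to current recruitment approaches". Section 9 (Statistical Aim 1) repeats that it will "shorten time to site activation for trials, and reduce unexplained variance in cognitive testing". The Aim 1 power paragraph names a 10% reduction in unexplained variance as scientifically meaningful.

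The analysis plan under Statistical Aim 1 drops the qualifier. It compares "the measured change and variance in cognitive scores to those in preclinical and prodromal studies for which similar data can be obtained", and the test is one of means "or variances (variance in cognitive testing) or corresponding resampling techniques will be used to detect differences between the TRC-PAD sample and comparator data".

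The power calculation rests on "a two-sided, one-sample t-test for means and a one-sample test of variance using the software PASS". Its result is: "A sample size of 2000 participants achieves 90% power to detect a difference of at least 0.4 points (5% change) in unexplained standard deviation". The Synopsis makes up that 2,000 as follows: "At least 2,000 (1,000 preclinical + 1,000 prodromal AD) trial-ready individuals aged 50-85".

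Section 9 opens with general provisions: a pre-specified SAP informed by a mid-study look at the data, including confounding; sub-group comparisons; and regression of the TRC-PAD metrics on covariates. None of these is tied to the variance test. The Aim 1 power paragraph closes by saying that looking at several sub-groups would not compromise power.

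**The concern.** A one-sample variance test with no model measures the spread of whatever scores it is given. In a cohort built from two disease stages, that spread includes the distance between the stage means as well as the variation left over within a stage. Only the second part can reasonably be called unexplained. Section 9 does not define the term, names no covariates for this test, and does not say how the comparator studies are to be matched on stage.

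At stake is whether this Aim 1 result can be interpreted. A real gain in precision could be masked because TRC enrolled a broader range of people than the comparator. An apparent gain could arise because the comparator was the more mixed of the two.

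**Working it through.** **Inputs from the documents (Section 9, Aim 1, and the Synopsis).** n = 2,000; two-sided alpha 0.05; 0.4 points is called a 5% change, so the implied SD is 0.4/0.05 = 8; meaningful effect 10% of variance; mix 50:50.

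**Inputs assumed.** The gap d between stage means, in comparator within-stage SDs, and the comparator's stage mix. Neither is in the documents, so a range is shown.

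**1. The plan's own figure.** For a one-sample chi-square test of variance with df = n − 1 and true variance ratio r,

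power to show a decrease = P(X < c_lo/r), with X chi-square on df degrees of freedom and c_lo its 2.5% point.

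With df = 1,999, c_lo = 1,877.0 and c_hi = 2,124.8. The observed variance must therefore fall below 0.939, or rise above 1.063, times the comparator value to be significant. An SD of 8 falling to 7.6 gives r = 0.95² = 0.9025 and power 89.8%. The stated 90% is reproduced. A 10% variance cut (r = 0.90) has power 91.3%.

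**2. What a stage mix adds.** With a proportion p in one stage,

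total variance = within-stage variance + p(1 − p)d².

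For p = 0.5 the added term is d²/4. The comparator within-stage variance is set to 1.

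**3. Single-stage comparator (assumed).** With no true change, r = 1 + d²/4. With a true 10% cut, r = 0.90 + d²/4.

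| d | Inflation d²/4 | r with true 10% cut | Power to show the cut | False increase, no true change |
|---|---|---|---|---|
| 0 | 0 | 0.900 | 91.3% | 2.5% |
| 0.25 | 1.6% | 0.916 | 79.1% | 7.2% |
| 0.5 | 6.3% | 0.963 | 22.1% | 49.1% |
| 1.0 | 25% | 1.150 | about 0% | over 99.9% |

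The true cut is cancelled exactly when d²/4 = 0.10, that is d = 0.63. At d = 1.0 with the true cut, the test declares a significant increase with probability 99%.

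**4. Comparator with the same 50:50 mix (assumed).** r = (0.90 + d²/4)/(1 + d²/4). With no true change r = 1 and the type I error is 5%. With the true cut, r = 0.906 at d = 0.5 (power 87.5%) and r = 0.920 at d = 1.0 (power 74.5%).

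**5. Comparator with 80% in one stage (assumed).** The comparator's own added term is 0.8 × 0.2 × d² = 0.16d². With no true change the rejection rate is 10.6% at d = 0.5 and 66.3% at d = 1.0.

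**6. Power after a repair.** Stage-adjusted residual variance pooled over 2,000 (df about 1,998): 89.8% for a 5% SD cut and 91.3% for a 10% variance cut. Separate tests by stage (n = 1,000, df = 999): 61.9% and 64.3%. The smallest SD cut detectable with 90% power at n = 1,000 is about 7.0%.

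All these figures treat scores as normal and the comparator variance as a known constant, as the plan's one-sample calculation does.

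**The case against.** The strongest reply is that the documents never say the test uses total variance of pooled scores. The meaningful effect is stated for unexplained variance, and the power sentence speaks of "unexplained standard deviation of cognitive scores, assuming a type I error rate of 5" percent. The benchmark variability is described as within a site, so some between-site spread appears to be set aside already. Section 9 also anticipates an SAP that considers confounding, allows sub-group and covariate analyses, and for Aim 2 separates out prodromal comparators. On this view the plan is unfinished rather than wrong.

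Much of that stands. Pooling is an inference from the sample size, the test named and the absence of a model. The general provisions do not close the gap, because none is linked to the variance test. Aims 2 and 3 name their models; Aim 1 names none for variance.

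A reader might go further and infer that stage mix, rather than test precision, will decide the result, or that the test cannot answer Aim 1 whichever way it comes out. The documents do not support that. It requires a large stage gap and a comparator of different mix, and neither is given. At d = 0.25 a true 10% cut is still found in 79% of cases against a single-stage comparator, and a comparator of the same mix produces no false signal. Nor do the documents say that the comparator studies each cover a narrower range than TRC.

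**Conclusion.** The concern holds in a limited form. Unexplained variance is the stated target but is undefined, and the only test named for it carries no residual model, stage term or stage matching. Following the text as written lets case mix confound the comparison. The stated 90% power is arithmetically sound; the gap lies in what is being tested.

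The size is uncertain. Under a single-stage comparator it runs from a modest loss of power (91% to 79% at d = 0.25) to complete masking with a false increase (d = 1.0). Under a comparator of the same mix it is dilution only. Should-fix is the right grade: Section 9 calls the aims exploratory, this test did not set the sample size, and variance is one of three Aim 1 claims.

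**What to change.** In the Aim 1 analysis plan, define unexplained variance as the residual variance of the baseline (pre-trial) cognitive score after adjustment for stage, and for age, education and site where the comparator data allow. Compare it with the same quantity on the same instrument in stage-matched comparators, and report the variance ratio with a bootstrap 95% CI. Settle the definition, covariates, instrument and comparators before the comparison is run. Keep to the baseline score: a residual from repeated scores with a participant random effect would be a different quantity from the baseline variability on which the plan is powered.

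Pooling the stage-adjusted residual over 2,000 keeps about 90% power for a 5% SD cut. If the test is run separately by stage (n = 1,000), state that power is about 62% and correct the sentence saying that sub-groups would not compromise power.

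The cost is SAP wording and one simple model per data set. The real downside is fewer usable comparators: only those with participant-level data or stage-specific SDs on the same instrument qualify. Where only a published SD is available, adjustment beyond stage is not possible and the report should say so.

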5.4 CLINICAL TRIAL PARTICIPATION AND TRC STATUS

Individuals enrolled into TRC and then screened for clinical trials are placed on temporary inactive status at the time of consent for the clinical trial. Data regarding clinical trial screening and participation will be reported in the eCRF. Upon completion of trial activities, participants are reactivated in TRC, resuming 6 months visits as per the SOA.

The Site PI may request from the Medical Monitor that he/she be provided amyloid testing results to inform pre-screening for a specific trial protocol. In some cases, certain screening procedures may need to be repeated at the time of re-entry into TRC. Consult with the Coordinating Center for guidance on a case-by-case basis.

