8.1.2 SCREENING

The purpose of the Screening Visit is to further determine eligibility for the TRC cohort and to complete the informed consent. The screening procedures will be conducted as outlined in the Schedule of Activities (section 1.3).

Procedures may be performed on separate days as long as all procedures are conducted within the visit window. Screening Stages 1 and 2 must be completed within a 60-day window. Screening stage 3 should be completed within 84 days of the start of screening activities. It is acceptable to delay some assessments if the study cannot be properly conducted due to the COVID-19 pandemic. In these cases, reach out to the Coordinating Center for additional guidance.

Screening Stage 1 data will be centrally reviewed prior to site being authorized to proceed with Stage 2 (amyloid testing via PET or CSF) and again prior to the site being authorized to proceed with Stage 3 (eligibility discussion). Sites may not proceed with Stages 2 or 3 of screening until authorized.

If a female is not surgically sterile or post-menopausal by two years, a pregnancy test will be performed locally at the site prior to conducting the PET scan. Participants with positive pregnancy test will be ineligible for amyloid PET imaging.

Screening visit procedures may be repeated if clinically necessary (e.g. to follow-up on an abnormality identified on clinical labs) or if data from the initial procedure is not analyzable (e.g. PET scan QC failure).

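### Aim 1 tests recruitment timeline against 120 days with no defined clock, using a one-sample mean test that cannot include members not yet placed in a trial

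*Combined protocol and SAP*

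**What the plan says.** All of Aim 1's analysis is in section 9 of the combined protocol and SAP.

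- Method: "Two-sided, one-sample tests of means (recruitment timelines and time to site activation") or corresponding resampling techniques, set against comparator data from preclinical and prodromal studies that are not named. On the significance level: "A p-value of 0.05 will be used to conclude significant differences between the two study groups".
- Target: "A reduction of 10% in mean recruitment timeline, mean time to site activation and unexplained variance in cognitive testing is considered scientifically meaningful".
- Power: "A sample size of 2000 participants achieves 90% power to detect a change as little as 3 days (3%) in recruitment timelines". The same sentence makes this claim for site activation as well, and the basis given for both is "assuming current estimates of 120+/-40 days respectively".
- Timing: "All statistical analyses will be conducted at the end of the grant cycle with all available data at the point of data cut-off date".

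Other sections bear on what a recruitment timeline could be.

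- Section 8.1.2: "Screening stage 3 should be completed within 84 days of the start of screening activities". The same section accepts COVID-19 delays.
- Section 8.1.1: most people first enrol in the APT Webstudy and are referred once flagged as at risk. No time limit is given for this, and those with known amyloid status may bypass it.
- Section 5.4: members go inactive when they consent to a trial, and "Data regarding clinical trial screening and participation will be reported in the eCRF".
- Section 5.5 expects entry to TRC throughout the study. Section 8.1.3 foresees members who stay a long time without entering a trial. Section 7.1 withdraws members who develop dementia.

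No section says which event starts or stops the recruitment timeline, in TRC-PAD or in the studies behind the 120 days.

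**The concern.** Faster recruitment is the lead claim of Aim 1, and the answer depends on which interval is measured. The power statement assumes 2,000 complete values. Every enrolled member has a complete value if the clock stops at TRC entry, but that interval has its own visit window. It also leaves out the wait in TRC and the therapeutic trial's own consent and screening. A clock that stops at trial entry fits the programme's purpose better, but members still waiting at the cut-off have no value, and they tend to be those with the longest waits. A mean over the rest is too short. Section 9 names no censoring or time-to-event method for this metric, although its Aim 3 plan does address missed measurements and loss to follow-up.

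**Working it through.** **1. The plan's own figure.** Inputs from section 9: n = 2,000, mean 120 days, SD 40 (reading ± 40 as an SD), two-sided 0.05, difference 3 days.

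- Standard error = 40/√2000 = 0.894 days.
- Power ≈ Φ(3/0.894 − 1.960) = Φ(1.394) = 91.8%, in line with the stated 90%.
- Detectable change at 90% power = (1.960 + 1.282) × 0.894 = 2.90 days, or 2.4% of 120. Three days is 2.5%.

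The arithmetic is sound. The question is what the 2,000 values are.

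**2. Clock from start of screening to TRC entry** (taking completion of Stage 3 as entry).

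- If the window is kept, the mean is at most 84 days, so the gap is at least 120 − 84 = 36 days, and 36/120 = 30%.
- The meaningful effect is 10% of 120 = 12 days, so the gap is at least 36/12 = 3 times that.
- Test statistic at SD 40: 36/0.894 ≈ 40.
- If the window slips: suppose overrunning members average L days and all others take exactly 84. The mean reaches 120 only when a share 36/(L − 84) overruns. That is 55% at L = 150, 37.5% at L = 180 and 23% at L = 240.

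**3. Clock ending at trial entry, placed members only.** Assumptions, not in the documents: entry uniform over T = 1,825 days, cut-off at day T, exponential waits with mean M, no other exits. With a = T/M:

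- Share placed = 1 − (1 − e^−a)/a.
- Mean among the placed = (M/a)[a − 2 + (a + 2)e^−a] / share placed.

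| True mean (days) | Share placed | Values out of 2,000 | Observed mean (days) |
|---|---|---|---|
| 120 | 93.4% | 1,868 | 111.6 |
| 150 | 91.8% | 1,836 | 136.6 |
| 365 | 80.1% | 1,603 | 277.6 |
| 730 | 63.3% | 1,266 | 401.1 |

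At a true mean of 120 the simulated SD among the placed is 111.1, so z = (111.6 − 120)/(111.1/√1868) ≈ −3.3. A programme exactly as fast as the comparator would be declared faster. At a true mean of 150 the simulated z is +5.2, and the test still calls TRC-PAD slower.

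**4. Sensitivity of that bias.** When almost no wait exceeds T, the shortfall is approximately SD²/(T − M).

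- Exponential, M = 120: 120²/(1825 − 120) = 14,400/1,705 = 8.4 days, which is 70% of the 12-day meaningful effect.
- SD 40, M = 120: 1,600/1,705 = 0.9 days.
- Exponential, M = 130: 16,900/1,695 = 10.0 days, giving an observed 120.0. A programme truly 10 days slower would look equal.
- Entry closed at 3 years, exponential, no loss (simulated): a true 120 is observed as 119.9, but a true 365 as 318.5.
- Assumed loss of 20% a year, five-year entry (simulated): a true 120 is observed as 104.4 and a true 150 as 126.2.

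**5. Clock from Webstudy enrolment.** Nothing limits the time to referral, so the 84-day window does not bound it. Direct referrals may have no start date. The documents give no figure from which to compute a direction.

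**The case against.** A reader might infer that the protocol caps TRC entry at 84 days and that the test therefore favours TRC-PAD whichever clock is used. The documents do not support this. The window is worded as a should, accepts COVID-19 delays, and covers only start of screening to Stage 3. Webstudy time is unbounded, and a further clock, trial consent to trial enrolment, contains neither the window nor the long wait. On the trial-entry clock a downward bias is not a favourable verdict: in the table above, three of the four observed means exceed 120, so the test would report TRC-PAD as slower. A false finding of faster recruitment needs a true mean near 120 and widely spread waits. At the plan's own SD of 40 the bias is under a day.

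Nor can one say that the 120 days is mismatched, since the documents never say what it measures and restrict comparators to studies with similar data.

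It is also fair that section 9 defers detail to a SAP informed by a mid-study look at bias and missing data, calls the aims exploratory, and says the sample size was not chosen for this power.

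These points limit the size and direction of the problem. They do not supply a clock or a method. Choosing the clock after a mid-study look is what pre-specification should prevent, and the resampling alternatives that section 9 lists do not recover the missing waits.

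**Conclusion.** The point holds as a defect of definition and method. The recruitment timeline has no start or stop event on either side of the comparison, and the planned test has no place for members not yet placed. On a screening-to-entry clock with the window kept, the result is settled by the window: at least 36 days, or 30%, below 120. On a trial-entry clock fewer than 2,000 values are likely and their mean is biased short. The size depends on assumed waits and accrual: at a true mean of 120 days, from practically nil (entry closed at 3 years, no loss) through about 1 day (SD 40) and 8 days (exponential) to about 16 days (with 20% yearly loss), and far more for long waits. The bias is in TRC-PAD's favour but need not reverse the conclusion. On a clock from Webstudy enrolment the direction is unknown. The correction should be made because this is the programme's headline claim and the remedy is cheap. The exploratory status of the aims keeps it from being more serious.

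**What to change.** In section 9:

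- State the same start and stop events for TRC-PAD and for each comparator study before the data are examined, and report each clock separately.
- Do not test screening-to-TRC-entry time against 120 days unless the 120 days covers the same interval.
- For time to trial entry, replace the one-sample mean test with a time-to-event analysis of every enrolled member: cumulative incidence, or restricted mean time over a stated horizon. Censor at the cut-off and treat withdrawal, dementia and death as competing exits. Describe the result as including the wait for an available trial, since it reflects trial supply as well as recruitment efficiency.
- Limit the statement of 90% power for 3 days with 2,000 participants to a clock on which all 2,000 have a value, and withdraw it for time to trial entry.

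The cost is mainly wording. Section 5.4 already calls for trial screening and participation data in the eCRF. The only event it ties to a change of status is trial consent, so the sponsor should confirm that a trial enrolment date is captured if that is the chosen stop event. The downside is a longer reported TRC-PAD timeline and a less favourable power statement.

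### Aim 1 counts 2,000 participants from about 60 sites as independent, so its 3-day power claim, p-values and interval widths hold only if site has no effect

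*Combined protocol and SAP*

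**What the plan says.** The Aim 1 analysis plan in section 9 specifies "Two-sided, one-sample tests of means (recruitment timelines and time to site activation) or variances (variance in cognitive testing) or corresponding resampling techniques" to compare TRC-PAD with comparator data. On power it states: "Power analyses for these hypotheses were done using a two-sided, one-sample t-test for means and a one-sample test of variance using the software PASS". The result for the two timelines is that "A sample size of 2000 participants achieves 90% power to detect a change as little as 3 days (3%) in recruitment timelines" and in time to site activation, "assuming current estimates of 120+/-40 days respectively". A 10% reduction is called scientifically meaningful for each metric, which is 12 of 120 days for the timelines.

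For cognition, the comparator variability is said to "range between 4.5 and 10 points in ADASCog11 score within a site". The power claim is 90% for a 0.4-point (5%) change in the unexplained SD, again with 2,000 participants. Section 9 concludes that very small differences are detectable and that subgroup work would not compromise power.

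The synopsis (section 1.1) gives "Approximately 60 AD clinical trials sites". Section 9 mentions mixed models for covariate associations, for repeated measures within a participant (Aim 2) and for scores over follow-up (Aim 3). It gives no site term, ICC, design effect, cluster-robust error or site-level resampling for the Aim 1 tests.

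**The concern.** Participants at one site share what determines how fast they move through screening. The tracer depends on what the site can obtain (section 6), Stage 2 needs local PET or lumbar puncture, and eligible participants normally need an in-person discussion with a licensed clinician (section 8.1.2.3). If timelines are positively correlated within site, the one-sample standard error is too small. Power for small differences is then overstated, the 5% test rejects too often and the confidence intervals are too narrow.

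Two related gaps sit in the same paragraphs. Time to site activation is a property of a site, yet its power is computed with 2,000 participants. The cognitive SD to be tested is not defined as pooled or site-adjusted, although its comparator is a within-site figure.

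**Working it through.** **Inputs.** N = 2,000; mean 120 days, with the +/-40 read as an SD; two-sided 5% (all from section 9); 60 sites (section 1.1), so m = 2,000/60 = 33.3 per site. The ICC is my assumption (0.01, 0.05, 0.10), as are equal site sizes.

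**Reproducing the plan's figures.**
- Timelines: SE = 40/√2000 = 0.894 days. Power for 3 days from the one-sample t-test is 91.8%. The difference detectable with 90% power is (1.960 + 1.282) × 0.894 = 2.90 days. The stated 90% for 3 days therefore reproduces, but only with 2,000 independent values.
- Cognition: 0.4 points at 5% implies a reference SD of 0.4/0.05 = 8. The one-sample variance test for 8 against 7.6 has 89.8% power, which also reproduces.

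**Recruitment timelines with a site effect.** Design effect DE = 1 + (m − 1) × ICC; effective N = 2000/DE; SE = 40 × √(DE/2000). Power = Φ(3/SE − 1.96), for a test that uses the correct SE. Type I error of the unadjusted test = 2 × [1 − Φ(1.96/√DE)].

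| Assumed ICC | DE | Effective N | Power, 3 days | Detectable at 90% | Type I error, unadjusted test | True 95% CI width relative to unadjusted (√DE) |
|---|---|---|---|---|---|---|
| 0.01 | 1.32 | 1,511 | 83% | 3.3 days | 8.8% | 1.15 |
| 0.05 | 2.62 | 764 | 54% | 4.7 days | 22.6% | 1.62 |
| 0.10 | 4.23 | 472 | 37% | 6.0 days | 34.1% | 2.06 |

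For the 12-day target, even an ICC of 0.20 (DE 7.47, effective N 268) leaves 99.8% power.

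**Time to site activation.** With one value per site, n = 60 and SD 40, the one-sample t-test has 9% power for 3 days and 63% for 12 days. It detects 17.0 days (17.0/120 = 14%) with 90% power. Reaching 90% power for 12 days would take 119 sites.

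**Cognitive SD, if it is pooled over sites.** Pooled SD = within-site SD/√(1 − ICC). A true 5% fall, from 8 to 7.6 within site, gives a pooled SD of 7.6/√0.95 = 7.80 at ICC 0.05 and 7.6/√0.90 = 8.01 at ICC 0.10. The fall is cancelled exactly at ICC = 1 − 0.95² = 0.0975. In a simulation of 60 sites (4,000 runs), the pooled test detected the fall in 81%, 37% and 4% of runs at ICC 0.01, 0.05 and 0.10. A test on the within-site residual SD kept 88% to 90%.

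**The case against.** The best defence has four parts.

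- **The plan leaves room for a site-level analysis.** Section 9 calls the aims exploratory, promises estimates with intervals, allows resampling and defers detail to an SAP. This does not settle the point. Exploratory status is used only to waive multiplicity adjustment, while the plan still promises formal hypothesis tests at 0.05. Resampling participants rather than sites keeps the same flaw, and nothing says that sites will be resampled.
- **Sites could be treated as fixed.** If conclusions were confined to this selected network, the unadjusted SE would not be too small. But Aim 1 is about an approach meant to speed up future trials, so its conclusions are meant to reach beyond these sites.
- **The ICC is unknown.** This stands. Recruitment timeline is not defined in section 9, and parts of the pathway are central, such as Webstudy referral and the review before Stages 2 and 3. The direction holds for any positive ICC; the size is conditional.
- **Unexplained SD may already mean a residual after site.** This also stands. A reader might infer that the plan sets a pooled TRC SD against a within-site figure. The text never says pooled, and with a site-adjusted residual almost no power is lost. The supportable criticism is that the quantity is undefined.

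It is also true that the cohort size was chosen to support an efficacy trial, not from this power calculation.

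**Conclusion.** The point holds for the timelines. The stated 90% power for a 3-day change in recruitment timelines needs complete independence across sites. Under an assumed ICC of 0.01 to 0.10, the 90% detectable difference is 3.3 to 6.0 days, and the unadjusted test's error rate is 9% to 34%. These rest on 60 equal sites and an SD of 40 days; unequal site sizes would generally make them worse.

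A reader might infer that Aim 1 is underpowered for its own recruitment target. The documents do not support that: 12 days keeps more than 99% power up to an ICC of 0.20. What fails is the 3-day claim, the assurance about very small differences, the p-values and the interval widths.

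Activation time is where the 10% target itself is short of power: 63%, with no ICC needed. This assumes one value per site. If sites are activated for several trials there would be more values, but reaching 2,000 would take about 33 activations per site, still clustered.

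For cognition, the finding is an undefined quantity. Masking of a true reduction is a consequence only if the SD is pooled. Nor would site adjustment alone make the comparison valid: the comparator is ADASCog11, and TRC collects the PACC (sections 1.3 and 8.1.7).

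**What to change.** In section 9 and the SAP:

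- **Recruitment timelines.** Define the interval. Analyse it with a random intercept for site, or with site-cluster-robust or cluster-bootstrap standard errors. If resampling is used, resample sites.
- **Time to site activation.** Make the site the unit of analysis, and account for repeated activations at a site if there are any.
- **Power.** Restate it over an ICC range. For example: with 2,000 participants at 60 equal sites, SD 40 days and ICC 0.01 to 0.10, 90% power for about 3.3 to 6.0 days; with one activation time at each of 60 sites, 63% power for 12 days and 90% for about 17 days. Withdraw or qualify the statement about very small differences and subgroups.
- **Cognition.** Define the unexplained SD as the within-site residual SD from a model with a site effect. Name a comparator on the same instrument, or a standardised comparison with its scale set in advance.

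The timeline changes cost wording and a less favourable detectable difference. Site is already recorded, so they need no new data. The cognitive comparison also needs comparator data on a matching instrument; the documents do not show whether such data are available.
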